3.5. Determination of Sample Size

A sample size of 75 subjects per group will provide >80% power to detect difference between groups of 3 points on change from baseline the Yale Global Tic Severity Scale-Total Tic Score (YGTSS-TTS), with standard deviation = 6.1 and alpha = 0.05, assuming 10% drop out.

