3.6. Treatment Assignment & Blinding

Subjects will be randomized 1:1 to either ecopipam or matching placebo. Randomization will be stratified by weight band (\geq 18 to \leq 23 kg, >23 to \leq 34 kg, >34 to \leq 44 kg, >44 to \leq 68 kg, >68 to \leq 83 kg, >83 kg).

Throughout the study, subjects and all personnel involved with the conduct and interpretation of the study, including the subject, parents/guardians, investigators, site personnel, and sponsor staff will be blinded to the treatment codes. Randomization data will be kept strictly confidential, filed securely by an appropriate group with the Sponsor or Syneos and accessible only to authorized persons (e.g., Safety) until the time of unblinding.

A master list of all treatments and the subject numbers associated with them will be maintained electronically by the unblinded clinical supply vendor and the unblinded personnel at Syneos. The process to request unblinding and the randomization code will be outlined in a separate document. The site will be trained in this process and it should be used only in an emergency. These codes should only be broken if knowledge of the subject's randomization code will affect his/her medical treatment. If possible, before breaking the blind, the Investigator should consult with the Sponsor to ascertain the necessity of breaking the code. The Investigator is to record the date and time of requesting the code and the reason for breaking the code.

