In the event that statistical significance in favor of ecopipam is determined from the primary analysis, subjects in the ecopipam group with a missing YGTSS-TTS score (change from baseline) will be assigned successively more extreme values, whilst subjects in the placebo group with a missing YGTSS-TSS score (change from baseline) will be assigned successively less extreme values, to find the point at which statistical significance is lost (i.e. the 2-sided P-value becomes greater than 0.05)

Details for tipping point analysis are described below:

- a. For patients that completed the study, intermittent missing data are considered as MAR and will be imputed by predictive mean matching multiple imputation method (Heitjan and Little 1991, Schenker and Taylor 1996). The imputation model will include age group at baseline, region, treatment arm, baseline TTS score, and TTS scores at all visits up to the imputed visit where the TTS is scheduled to be collected.
- b. For patients who discontinued due to any reason, all missing data will be imputed using the same predictive mean matching multiple imputation method. The imputed values will be adjusted under MNAR assumption:
 - Patients randomized to ecopipam: the first missing value after patients dropout will be analyzed assuming the unobserved outcome is on average worsened by ō1 (where ō1 = 1 to 10 or estimated treatment effect, whichever is higher, in step of 1) compared to the patients who have no missing value;
 - Patients treated by placebo: the first missing value after patients dropout will be analyzed assuming the unobserved outcome is on average better by 52 (where 52 = 1 to 10 or estimated treatment effect, whichever is higher, in step of 1) compared to the patients who have no missing value;

The penalty or reward will not be applied to the values from later time points as these values are penalized or rewarded through condition on previous time points. For each combination of ($\overline{0}1$, $\overline{0}2$), 100 imputed datasets will be obtained.

c. The resulting complete, imputed datasets will each be analyzed using the same model as the primary analysis model, and the resulting statistics combined using methodology provided by Rubin (1987) and Little and Rubin (2002).

The complete multiple imputation methodology, along with SAS code, is detailed in Appendix (Section 14.5).

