10.10. COVID-19 Analyses

Due to COVID-19 pandemic, additional analyses will be conducted:

- Listings of COVID-19 related study disruptions by subject and by site, including descriptions of the disruption.
- The amount of missing data by treatment group and overall by endpoint for data missing due to COVID-19 will be summarized in a table.
- Protocol deviations due to COVID-19 will be summarized by type and treatment in a table.

11. Interim Analyses

An unblinded interim analysis will be conducted when approximately 50% of the 150 planned subjects have been randomized (1:1 ratio between ecopipam and placebo) and completed treatment or are terminated early. The interim analysis will be performed by an independent statistician and governed by an external Data Safety Monitoring Board (DSMB). The conditional power will be calculated to help the DSMB assess the probability of a successful study based on observed data.

The primary efficacy endpoint of the study is the YGTSS-TTS. A smaller YGTSS-TTS score indicates a better condition in subjects with Tourette's syndrome, and we may expect that the ecopipam group has a larger reduction than the placebo group. Let μ_{σ} be the mean change YGTSS-TTS score from Baseline to Week 12 for the ecopipam group, and μ_p be the mean change YGTSS-TTS score from Baseline to Week 12 for the placebo group. Then, given $H_0: \mu_{\sigma} \ge \mu_p \equiv \Delta_{\sigma-p} \ge 0$ vs. $H_1: \mu_{\sigma} < \mu_p \equiv \Delta_{\sigma-p} < 0$. Since the original sample size calculation is based on two-sided test at a significance level of α =5%, we will use $\alpha/2$ =2.5% to match the one-sided test.

The primary endpoint will be analyzed with a Mixed Model for Repeated Measures (MMRM) model using the SAS MIXED procedure with REPEATED statement. The model will include fixed effects for treatment, visit, visit interaction between treatment and visit, region, age group (0 = children 6-11, 1 = adolescents 12-17) and covariate for baseline YGTSS-TTS.

To determine if the total sample size should be increased from N (to N^*), the conditional power based on the MMRM will be calculated at the interim analysis using the observed effects (where n=75) and the planned sample size (N=150).

If it is determined that the sample size should be increased, the CHW (Cui-Hung-Wang) statistic, which controls the type I error, will be used. The CHW statistic is a weighted statistic defined as:

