14.5. Tipping Point Analysis

Let delta1 and delta2 be the penalty to ecopipam group and reward for placebo group, respectively. Delta1 and delta2 = 1 to 10 (or estimated treatment effect from primary analysis if it is larger than 10) in step of 1. General steps for this analysis includes:

Step 1:

For each combination of (delta1, delta2), 100 imputations will be created.

In order to induce monotonicity, an imputation model will first be used to impute missing values for TTS of the YGTSS week 4 change values and will use age group at baseline, treatment arm, and baseline TTS score to determine the scores.

The SAS code for the imputation is as follows:

```
proc mi data=final out=mi seed=666 nimpute=100;
class agegrp region1 arm;
var agegrp region1 arm base _4;
monotone regpmm; run;
```

* Create delta1, delta2 in the dataset;

```
data mitv1;
set mi;
do i=1 to 10;
do j=1 to 10;
delta1=i; delta2=j; output;
end;
end;
run;
```

```
data mitv1;
set mitv1;
if firstdrp=4 and missdm in ("MNAR') and index(arm, 'ecopipam') then _&cv=_&cv+delta1;
else if firstdrp=4 and missdm in ("MNAR') and arm='Placebo' then _&cv=_&cv-delta2;
run;
```

For each visit after week 4: %macro tippimp (cv, pv, pvs, seed);

```
proc mi data=mitv&pv out=mitv¤tv seed=&seed nimpute=1;
class agegrp region1 arm;
var agegrp region1 arm base _&cv &pvs;
monotone regpmm;
by _Imputation_ &delta1 &delta2; run;
data mitv&cv;
```

```
if firstdrp=&cv and missdm in ("MNAR') and index(arm, 'ecopipam') then _&cv=_&cv+delta1;
else if firstdrp=&cv and missdm in ("MNAR') and arm='Placebo' then _&cv=_&cv-delta2;
run;
%mend;
```

```
% tippimp (6, 4, _4 , 2626);
% tippimp (8, 6, 4, %str(_4 _6), 2828);
% tippimp (12, 8, 6, 4 %str(_4 _6 _8), 2929);
```

Step 2

The resultant complete data sets will be analyzed using the same model as the primary analysis. The SAS code is as follows:

proc sort data=mitv12; by delta1 delta2 _imputation_ descending arm avisitn; run;

proc mixed data=all order=data; by delta1 delta2 _imputation_; class usubjid arm avisitn agegrp region1; model chg=arm avisitn arm*avisitn agegrp region1 base / ddfm=sat; repeated avisitn / type=un subject=usubjid; Ismeans arm*avisitn / diff cl; ods output diffs=diff(where=(avisitn=_avisitn) Ismeans=Ism; run;

```
Step 3
```

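### The tipping-point shift is added only at the first missed visit, so part of it is lost before Week 12 and the capped grid can miss the point it is meant to find.

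*SAP*

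**What the plan says.** SAP 8.1.2.1, item 3, runs the tipping-point analysis only if the primary analysis favours ecopipam significantly. Its aim is "to find the point at which statistical significance is lost". Dropouts' missing scores are imputed by predictive mean matching. Delta1 then worsens the ecopipam value, and delta2 improves the placebo value, at the first missed visit after dropout. Later visits are left alone: "The penalty or reward will not be applied to the values from later time points as these values are penalized or rewarded" through conditioning on the earlier ones.

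SAP 14.5 does the same in code: the shift fires only when the first dropout visit equals the visit being imputed. The grid is "Delta1 and delta2 = 1 to 10" in steps of 1, extended only if the estimated effect exceeds 10, and the printed loops stop at 10. The imputation step for visits after Week 4 uses "var agegrp region1 arm base _&cv &pvs;" with a MONOTONE statement.

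The primary endpoint is the change to Week 12 (SAP 4.1). YGTSS is scored at Weeks 4, 6, 8 and 12 (SAP 8.1.1), and the mITT set requires at least one post-baseline score (SAP 5.3). The SAP does not say what to report if no pair tips, and does not ask for the shift achieved at Week 12.

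**The concern.** The result is judged at Week 12, but for anyone who drops out before Week 8 or Week 12 is due, delta is applied at an earlier visit. Week 12 then receives only what the imputation regression passes on, which is less than the whole at any between-visit correlation below 1. A reader who sees that significance survived a delta of 10 in both arms will take 10 as the Week 12 shift. The stress actually tested is smaller, by an amount that is not reported and that depends on correlation and dropout timing. With a capped grid, a finding that nothing tipped could come partly from the algorithm rather than from the data.

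The code adds a second problem. PROC MI's MONOTONE method imputes each variable from those listed before it. With the current visit listed ahead of the earlier visits, the shifted scores are not among its predictors, so the carry-over that 8.1.2.1 relies on would be absent or the step would fail.

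**Working it through.** **1. Planning figures.** SAP 3.5: "A sample size of 75 subjects per group will provide >80% power to detect difference between groups of 3 points", "with standard deviation = 6.1 and alpha = 0.05, assuming 10% drop out". Allocation is 1:1 (SAP 3.6) and the test is two-sided at 5% (SAP Section 11).
- Evaluable per arm: 75 × 0.9 = 67.5.
- SE of the difference: 6.1 × √(2/67.5) = 1.05.
- Power: Φ(3/1.05 − 1.96) = 81.5%, so the stated figure is reproduced.
- Smallest significant difference: 1.96 × 1.05 = 2.06.
- Erosion needed to lose significance: 3.0 − 2.06 = 0.94, or 3.5 − 2.06 = 1.44.

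**2. Share of delta reaching Week 12.** This is the coefficient of the first missed visit in the regression of Week 12 on the history up to that visit. The documents give no correlations, so r = 0.5-0.9 is assumed.
- Compound symmetry with k predictors: r/(1 + (k−1)r).
  - Week 6 first missed: 0.33-0.47 (k = 2, Weeks 4 and 6), or 0.25-0.32 with baseline added, as in the code (k = 3).
  - Week 8 first missed: 0.25-0.32 (k = 3), or 0.20-0.24 with baseline (k = 4).
- AR(1) by visit number: r² = 0.25-0.81 for Week 6 and r = 0.50-0.90 for Week 8.
- Week 12 first missed: 1.00.

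A monotone dropout in the mITT set has a Week 4 score, so Week 4 as first missed visit is left out.

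**3. Average share, with dropout even over Weeks 6, 8 and 12 (assumed).**
- Lowest: (0.25 + 0.20 + 1)/3 = 0.48.
- Highest: (0.81 + 0.90 + 1)/3 = 0.90.
- A nominal 10 therefore averages about 5-9 points at Week 12.

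**4. Erosion at (10,10), 10% missing per arm.** Erosion = 0.10 × (10 + 10) × average share.

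| Case | Erosion |
|---|---|
| SAP rule, compound symmetry | 0.97-1.20 |
| SAP rule, AR(1) 0.5 / 0.6 / 0.7 / 0.8 / 0.9 | 1.17 / 1.31 / 1.46 / 1.63 / 1.81 |
| Shift applied at Week 12 | 2.00 |

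- Observed 3.0 (0.94 needed): every case tips. Break-even average share is 0.94/2 = 0.47.
- Observed 3.5 (1.44 needed): the direct shift tips. The SAP rule does not under compound symmetry or AR(1) of 0.6 or lower. Break-even share is 1.44/2 = 0.72.
- Observed 3.0, 5% missing, SE held at 1.05: the SAP rule erodes 0.48-0.90 and the direct shift 1.00, against 0.94. Recomputing the SE with 71.25 per arm raises the need to about 1.00, so the direct shift then only just reaches it.

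**5. Simulation.** Predictive mean matching, 75 per arm, true effect 3, compound symmetry 0.6 and 0.8, AR(1) 0.7 and 0.85, 15 imputations, and Week 12 ANCOVA in place of MMRM. There were 120 trials per scenario, 90-100 of them significant; simulation error is about 5 percentage points.
- Retained share: 0.35-0.64 (Week 6), 0.27-0.78 (Week 8), about 1.0 (Week 12).
- With 8 dropouts per arm, (10,10) removed significance in 40-75% of significant trials under the SAP rule, against 87-91% with a direct Week 12 shift.
- With 12 dropouts per arm: 71-94% against 99-100%.

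**6. Code.** SAP 14.3 and 14.4 list visits in ascending order; 14.5 puts `_&cv` before `&pvs`. The macro takes four arguments, but the Week 8 and Week 12 calls pass five, so `&pvs` receives 4 or 6 instead of the visit list. If the step ran with no carry-over, only those first missing Week 12 would count and (10,10) would erode 0.10 × 20 × 1/3 = 0.67.

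**The case against.** The SAP openly defines delta as a shift at the first missed value, and a sequential conditional shift is a recognised method. Its refusal to add delta again at later visits avoids double counting: on the structures above, adding it at every missed visit would give Week 12 120-271% of delta for subjects first missing Week 6 or 8. All of that stands. The fault lies in reading delta as a Week 12 shift and in capping a grid whose Week 12 effect is not reported.

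The cap can also fail without any fade. In the simulation with 8 dropouts per arm, 9-13% of significant trials did not tip even with the shift at Week 12. Some non-tipping is therefore real robustness, and ten points per arm is already more than three times the planned effect.

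A reader might infer that no ecopipam-only penalty is examined anywhere, because both deltas start at 1. The documents do not support that: the jump-to-reference analysis imputes ecopipam dropouts as placebo, and the MAR imputation is essentially the (0,0) point. Starting at 0 is tidiness within this grid.

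The appendix code looks like a draft. It also uses an undefined macro variable and has a data step with no SET statement, and its layout comes from a PDF. The text of 8.1.2.1 governs and plainly intends conditioning on earlier visits. A failed step would be noticed, so the 0.67 figure is conditional and not a prediction. The mismatch should still be corrected before the code is used.

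**Conclusion.** The point holds as a limited one. The first-visit shift fades for subjects first missing Week 6 or 8, a nominal 10 averages about 5-9 points at Week 12, and the capped grid can miss a tipping point that the same delta at Week 12 would find. The size rests on assumed correlations of 0.5-0.9 and even dropout over Weeks 6, 8 and 12. If all dropouts first missed Week 12, there would be no fade.

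Three stronger inferences are not supported:
- That a delta of 10 amounts to only a few points at Week 12 in general. Shares that low apply to some early dropouts, not to the average.
- That the grid cannot tip. At the planned 3.0 points with 10% dropout the (10,10) corner tips in every case computed, though narrowly at low retention.
- That the primary result is compromised. The analysis follows a significant primary test and affects only the statement about robustness.

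**What to change.** - Define delta as the shift in the imputed Week 12 score, applied once. Do not add it at every missed visit under sequential conditioning, because it accumulates. Alternatively, keep the sequential rule and report the mean Week 12 shift achieved in each arm for every (delta1, delta2) pair.
- In 14.5, put `&pvs` before `_&cv` in the VAR statement and correct the Week 8 and Week 12 macro calls, so that the code does what 8.1.2.1 describes.
- Start both deltas at 0. Extend the grid until significance is lost or a justified limit is reached, and state what will be reported if that limit is reached first.

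The cost is a few lines of code and a short SAP edit, with a possibly less favourable robustness statement.

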Summary statistics will be presented along with a full data listing by treatment group.

8.2.2. Change in Clinician Global Impression Tourette Syndrome of Improvement (CGI-TS-I) from Baseline to Week 12

The CGI consists of two reliable and valid 7-item Likert scales used to assess severity and change in clinical symptoms. The improvement scale (CGI-TS-I) will be used at every visit after the Screening and Baseline Visits. The scale ranges from 1 = "very much improved" to 7 = very much worse." The CGI severity scale (CGI-TS-S) will be used at each study site visit and ranges from 1 = "not ill at all" to 7 = "among the most extremely ill."

A secondary analysis will be performed on the CGI-TS-I at Week 12.

Statistical analysis:

The analysis method will be the same as the primary efficacy analysis as described in **Section 8.1.1**, with the exception of no baseline score will be used as a covariate.

Summary statistics will be presented along with a full data listing by treatment group.

8.2.3. Change in YGTSS-Global Score (GS) from Baseline to Week 12

A secondary analysis will be performed on the change in YGTSS-Global Score (YGTSS-GS) from Baseline to Week 12.

Statistical analysis:

The analysis method will be the same as the primary efficacy analysis as described in Section 8.1.1.

Summary statistics will be presented along with a full data listing by treatment group.

8.2.4. Change in Caregiver Global Impression of Change (CaGI-C) from Baseline to Week 12

The CaGI-C scale is a 7 point Likert scale that asks the caregiver the following question: overall, how have the patient's symptoms changed (if at all) since the beginning of the study (before starting treatment)? The CaGI-C is rated as follows: 1 (very much improved), 2 (much improved), 3 (minimally improved), 4 (no change), 5 (minimally worse, 6 (much worse), and 7 (very much worse).

A secondary analysis will be performed on the change in CaGI-C from Baseline to Week 12.

Statistical analysis:

The analysis method will be the same as the primary efficacy analysis as described in **Section 8.1.1**, with the exception of no baseline score will be used as a covariate.

Summary statistics will be presented along with a full data listing by treatment group.

8.2.5. Change in Gilles de la Tourette Syndrome – Quality of Life Scale for Children and Adolescents (C&A-GTS-QOL) from Baseline to Week 12

Gilles de la Tourette Syndrome–Quality of Life Scale for Children and Adolescents (C&A-GTS-QOL) is a patient-reported health related quality of life measure developed for children and adolescents. The C&A-GTS-QOL is a 27-item questionnaire specific to TS patients that asks the patient to assess the extent to which their quality of life is impacted by their symptoms. The C&A-GTS-QOL contains 6 subscales (cognitive, coprophenomena, psychological, physical, obsessive-compulsive, and ADL) and uses a 5 point Likert scale ranging from no problem to extreme problem. Patients will also be asked how satisfied they feel overall with their life at that moment by using a VAS scale between 0 and 100 (Su et al 2017). Following are the questions assessed in each C&A GTS QOL subscale:

- Cognitive (questions 11, 12, 13, 14, 18, 20, 21, 23) (range: 0-32)
- Psychological (questions 15, 16, 17, 19, 25, 27) (range: 0 24)
- Obsessive-compulsive (questions 7, 8, 9, 10) (range: 0 16)
- Physical (questions 1, 3, 4) (range: 0 12)
- Coprophenomena (questions 5, 6, 22) (range: 0 -12)
- ADL (questions 2, 24, 26) (range: 0-12)

Scores for the six subscales are generated by summing items and, for ease of interpretation,

transformation to a range of 0 to 100 (100x [(observed score - min possible score)/ (max possible score - min possible score)]). The total score, resulting from the sum of the subscale scores, is also normalized to a 0–100 range. For C&A GTS-QOL, if a response to 1 question is missing within the subscale, the missing response will be replaced with the average of the remaining responses within the subscale; if

responses to 2 or more questions within a subscale are missing, the missing responses will not be replaced and the subscale score will be set to missing; if at least 1 subscale is missing then the total score will be set to missing. For all analysis and summary, transformed scores will be used.

A secondary analysis will be performed on the change in C&A-GTS-QOL total score and VAS from Baseline to Week 12.

Statistical analysis:

The overall VAS score, QOL subscale scores for Cognitive, Psychological, Obsessive-compulsive, Physical, Coprophenomena, and ADL and the QOL total score will be analyzed using the same method as the primary efficacy analysis as described in 8.1 above.

Furthermore, summary statistics for the overall VAS score, QOL subscale scores for Cognitive, Psychological, Obsessive-compulsive, Physical, Coprophenomena, and ADL and QOL total scorewill be presented along with a full data listing by treatment group.

8.2.6. Percentage of subjects with a 25%, 50% or 75% improvement on the YGTSS-TTS

The percent of subjects with a 25% improvement on the YGTSS-TTS at any time between the Baseline visit and the Week 12 visit will be considered as a Response. Any subject who has at least 1 Response will be considered as a Responder; otherwise the subject will be considered a Non-Responder.

Statistical analysis:

The percentage of subjects with a 25% improvement on the YGTSS-TTS will be analyzed through a logistic regression model to obtain an estimate of the population odds ratio and associated confidence intervals between ecopipam and matching placebo. The model will include fixed effects for treatment, center, and covariate for baseline YGTSS-TTS score.

Summary statistics will be presented along with a full data listing.

Similar analyses will be performed for 50% and 75% improvement.

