13.2. Planned Analysis

13.2.1. Efficacy Analysis

The primary efficacy endpoint for this study will be the change from Baseline (score of YGTSS-TTS at Baseline) to end of therapy (score of YGTSS-TTS at Week 12). The analysis of primary efficacy endpoint will be performed in mITT and PP populations according to the randomized treatment.

The primary endpoint will be assessed with a Mixed Model for Repeated Measures (MMRM) model using (SAS MIXED procedure with REPEATED statement) with no imputation. The model will include fixed effects for treatment, visit interaction between treatment and visit, center, and covariate for baseline YGTSS-TTS score. If the sample size has been increased as a result of the interim analysis, the CHW (Cui-Hung-Wang) method will be used to control the type 1 error in the MMRM model. Taking consideration of missing data, multiple imputation or tipping point method may be used as a sensitivity analysis.

YGTSS-Global Score (YGTSS-GS), Clinical Global Impression of Tourette Syndrome Severity (CGI-TS-S), Clinical Global Impression of Tourette Syndrome Improvement (CGI-TS-I),

Caregiver Clinical Global Impression of Change (CaGI-C) and C&A-GTS-QOL will be analyzed using MMRM if appropriate. The treatment difference at Week 4, 8 and 12 can be estimated based on MMRM.

The percentage of subjects with a 25% improvement on the YGTSS-TS can be analyzed using Fisher Exact test.

All secondary endpoints will be analyzed in the mITT population according to randomized treatment.

All efficacy endpoints may also be summarized by treatment group. The fixed-sequence statistical strategy will be used to test all efficacy endpoints in a predefined rank order hierarchy which will be outlined in the SAP.

The full details and any sensitivity analyses will be specified in the SAP.

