8.2.7. Subjects with complete remission of tics on the YGTSS-TTS

Subjects with complete remission of tics on the YGTSS-TTS (i.e. YGTSS-TTS=0) at any time between the Baseline visit and the Week 12 visit will be considered as Responders. Any subject who has at least 1 Response will be considered as a Responder; otherwise the subject will be considered a Non-Responder.

Statistical analysis:

The percentage of subjects with complete remission of tics on the YGTSS-TTS will be analyzed through a logistic regression model to obtain an estimate of the population odds ratio and associated confidence intervals between ecopipam and matching placebo. The model will include fixed effects for treatment, center, and covariate for baseline YGTSS-TTS score.

Summary statistics will be presented along with a full data listing.

8.2.8. Change in YGTSS-TTS from Baseline to Weeks 4, 6, and 8

A secondary analysis will be performed on the change in YGTSS-TTS from Baseline to Weeks 4, 6 and 8.

Statistical analysis:

The analysis method will be the same as the primary efficacy analysis as described in **Section 8.1.1.**, with the treatment difference at weeks 4, 6, and 8 estimated based on MMRM.

Summary statistics will be presented along with a full data listing by treatment group.

8.2.9. Change in CGI-TS-S from Baseline to Weeks 4, 6, and 8

A secondary analysis will be performed on the change in CGI-TS-S from Baseline to Weeks 4, 6 and 8.

Statistical analysis:

The analysis method will be the same as the primary efficacy analysis as described in **Section 8.1.1.**, with the treatment difference at weeks 4, 6, and 8 estimated based on MMRM.

Summary statistics will be presented along with a full data listing by treatment group.

8.2.10. CGI-TS-I at Week 4, 6, and 8

A secondary analysis will be performed on the CGI-TS-I at Weeks 4, 6 and 8.

Statistical analysis:

The analysis method will be the same as the primary efficacy analysis as described in **Section 8.1.1.**, with the exception of no baseline score will be used as a covariate. The treatment difference at weeks 4, 6, and 8 will be estimated based on MMRM.

Summary statistics will be presented along with a full data listing by treatment group.

8.2.11. Change in YGTSS-GS from Baseline to Weeks 4, 6, and 8

A secondary analysis will be performed on the change in YGTSS-GS from Baseline to Weeks 4, 6 and 8.

Statistical analysis:

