The condition power will then be calculated under the following for the treatment difference δ and standard error $Var(\hat{\delta}_1)$:

3) Using the estimates from the stage 1 data. Treatment difference δ is the Stage 1 MMRM treatment effect (δ₁) and Var(δ₁) is the variance of this estimate of treatment difference based on the covariance matrix of the LSmeans.

Using these results, the DSMB may make one of the following recommendations:

- If the conditional power at the planned sample size (150) is less than 30% then the DSMB may recommend that the study be terminated for futility.
- 2) If the conditional power at the planned sample size (150) is greater than 30% and less than 80%, then the planned sample size will be increased up to 200 to try to achieve a conditional power of at least 80%. If the conditional power at the maximum sample size (200) is still less than 80%, the DSMB may recommend continuing the study at the maximum sample size (200).
- If the conditional power is at least 80%, then the DSMB may recommend continuing this study with the planned sample size (150).

Full details of the DSMB including primary responsibilities, its relationship with other study components, its membership, and the purpose and timings of its meetings are documented in a DSMB charter. These details will also include procedures to ensure confidentiality and proper communication, the guidelines to be implemented by the DSMB and an outline of the content of the closed reports (unblinded) and open reports (blinded) that will be provided to the DSMB.

12. Changes from Analysis Planned in Protocol

There are no changes from the analysis planned in protocol.

13. Reference List

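### SAP 8.2.6 and 8.2.7 give no sparse-event method for 75% tic improvement and complete remission, so an arm with no events leaves no finite odds ratio and an undefined test

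*SAP*

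**What the plan says.** SAP 8.2.6 counts a subject as a responder if the improvement threshold on the YGTSS-TTS is met at any visit up to Week 12. For 25% improvement the percentage "will be analyzed through a logistic regression model to obtain an estimate of the population odds ratio" and its confidence interval; the model contains treatment, center and baseline score. For the higher thresholds, "Similar analyses will be performed for 50% and 75% improvement". SAP 8.2.7 repeats the approach: "The percentage of subjects with complete remission of tics on the YGTSS-TTS will be analyzed through a logistic regression model", with the same terms. Neither section names the estimator, the test statistic, the type of interval, or what happens when events are few or absent.

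SAP 8.2 places these endpoints in the fixed testing sequence, after the primary and five other secondary endpoints and ahead of the Week 4, 6 and 8 endpoints. A non-significant step makes everything after it exploratory.

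Protocol 13.2.1 says: "The percentage of subjects with a 25% improvement on the YGTSS-TS can be analyzed using Fisher Exact test". It names no test for remission and leaves full details to the SAP. The protocol does not list 50% or 75% improvement as endpoints. SAP 12 states: "There are no changes from the analysis planned in protocol". SAP 6.5 rules out study site as a model factor and uses region.

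**The concern.** When one arm has no events, the logistic likelihood keeps rising as the treatment coefficient grows, so it has no maximum. The odds ratio and interval that the SAP asks for then do not exist. A program that reports a Wald test gives a p-value that moves towards 1 the longer it iterates, however strong the contrast. Fisher's, likelihood-ratio and Firth-penalised tests all remain defined on the same data and can give a very different answer.

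An empty placebo arm is a realistic outcome. From a baseline near 33, a 75% improvement is a fall of about 25 points. If it happens, passing or failing a confirmatory step depends on a software default or on a choice made after the data are seen.

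**Working it through.** **1. The plan's own figure.** SAP 3.5: "A sample size of 75 subjects per group will provide >80% power to detect difference between groups of 3 points", "with standard deviation = 6.1 and alpha = 0.05, assuming 10% drop out". Evaluable per arm: 75 × 0.90 = 67.5. With 67, SE = 6.1 × √(2/67) = 1.054, 3/1.054 = 2.847, and power = Φ(2.847 − 1.960) = 0.812. The statement is reproduced. It covers the primary endpoint only. The documents give no power or event rate for any responder step, so all rates in steps 2, 4 and 6 are assumptions.

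**2. Chance of an empty placebo arm.** P(0 events) = (1 − p)^75:
- 0.5%: 0.687
- 1%: 0.471
- 2%: 0.220
- 5%: 0.021

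**3. What the tests do with 8/75 vs 0/75** (treatment term only).
- Fisher: p = 0.006.
- Likelihood ratio: G² = 2[8 ln(8/75) + 67 ln(67/75) − 8 ln(8/150) − 142 ln(142/150)] = 11.54, p = 0.0007.
- Maximum likelihood with Wald, after 8, 12 and 20 Newton steps: coefficient 7.1, 11.1, 19.1; SE 11.5, 85, 4,641; p = 0.54, 0.90, 0.997.

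**4. How often this decides the step.** With placebo empty, Fisher is significant from 6 vs 0 (p = 0.028; 5 vs 0 gives 0.058). The share of trials that pass Fisher but have no finite odds ratio is therefore (1 − p_placebo)^75 × P(X ≥ 6), with X binomial(75, p_ecopipam). P(X ≥ 6) is 0.172, 0.561 and 0.773 at 5%, 8% and 10%. The last two columns enumerate all 2×2 tables; Wald uses treatment alone and counts an empty arm as a fail.

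| Ecopipam vs placebo | Passes Fisher, no finite odds ratio | Fisher passes | Wald passes |
|---|---|---|---|
| 5% vs 0.5% | 0.687 × 0.172 = 12% | 13% | 1% |
| 5% vs 1% | 0.471 × 0.172 = 8% | 9% | 1% |
| 5% vs 2% | 0.220 × 0.172 = 4% | 5% | 1% |
| 8% vs 1% | 0.471 × 0.561 = 26% | 36% | 11% |
| 10% vs 0.5% | 0.687 × 0.773 = 53% | 67% | 14% |
| 10% vs 1% | 0.471 × 0.773 = 36% | 57% | 22% |
| 10% vs 2% | 0.220 × 0.773 = 17% | 40% | 27% |
| 20% vs 5% | 2% | 76% | 78% |

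**5. Where the rates might lie.** Protocol 5.2.2.1 gives Day 30 falls in the earlier pediatric crossover study of 5.5 (SD 8.7) from 32.8 on ecopipam and 3.4 (SD 5.8) from 33.7 on placebo. A normal approximation at that one time point:
- 75% improvement, ecopipam: (24.6 − 5.5)/8.7 = 2.20, or 1.4%.
- 75% improvement, placebo: (25.3 − 3.4)/5.8 = 3.77, or 0.01%.
- Remission, ecopipam: (32.8 − 5.5)/8.7 = 3.14, or 0.1%. Placebo: essentially 0.

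Scoring a response at any visit raises these.

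**6. Any-visit simulation.** Assumptions: 75 per arm, baseline 33 (SD 7, at least 20), between-visit correlation 0.6, 10% dropout.
- Earlier study's changes: 75% response of about 6% vs 0.4%, Fisher power 20–23%; remission power about 0.
- Falls of 10 vs 5 points, same SDs: remission power 3–4%.
- Falls of 12 vs 4 points, same SDs: remission power 14–17%.
- Planned 3-point difference with SD 6.1 in both arms: Fisher power close to 0 for both 75% and remission.

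**7. The center term.** Protocol synopsis: about 60 sites, so 150/60 = 2.5 subjects per site. In 300 simulated trials at 10% vs 1%, adding 60 center effects to the logistic model raised the share with a non-finite treatment odds ratio from 44% to 61%. It cut the Wald pass rate from 24% to 14%.

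**The case against.** The strongest reply is that the documents prescribe neither maximum likelihood nor a Wald test. They say only that a logistic model is used. A likelihood-ratio test from that model is significant for 8 vs 0, so an infinite odds ratio does not by itself make the step impossible to pass. That stands, and it limits the point to an unstated choice. It does not remove the point: the estimate and interval requested still do not exist. The likelihood-ratio test is also not a safe default here. It rejects already at 3 vs 0 (G² = 4.22, p = 0.040), and enumeration with both true rates at 2% gives a 8.6% rejection rate at nominal 5%.

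A reader might also infer that the protocol's own test is Fisher's at 75% and remission, and that the SAP contradicts it there. The protocol does not support this. Its Fisher sentence is permissive and covers 25% only. At 25% no arm was empty in the simulations, so the documented mismatch and the sparse-event problem concern different endpoints.

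Finally, a reader might infer that the logistic model is what stops the sequence and that Fisher would rescue the later steps. The figures do not support this either. Remission follows directly after the improvement thresholds, Fisher needs at least 6 vs 0 there too, and it reached that in at most about 17% of simulated trials. These are also late secondary steps in a Phase 2b trial.

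**Conclusion.** The concern holds as an under-specified analysis with a concrete failure. Followed literally, SAP 8.2.6 (75%) and 8.2.7 can yield no odds ratio or interval and leave a confirmatory step to an open choice of test.

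The size depends on assumed rates. With ecopipam at 5–10% and placebo at 0.5–2%, the share of trials that pass Fisher without a finite odds ratio is 12% at 5% vs 0.5% and 36% at 10% vs 1%. Over the whole grid it runs from 4% to 53%. It is about 2% when placebo is at 5%. It is near zero when both rates are very low, because events are then too few for Fisher as well. That is the likely position for remission, and for 75% improvement under the planned 3-point difference.

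The claim that these steps often cannot be passed because of the logistic model goes further than the documents allow, since they give neither the rates nor the test.

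Two textual points need no assumption. The move from Fisher to logistic regression at 25% is not declared in SAP 12, and the center term in 8.2.6 and 8.2.7 conflicts with SAP 6.5. The primary analysis is not affected.

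**What to change.** Before unblinding, amend the SAP as follows.

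- **8.2.6 (75%) and 8.2.7:** take the confirmatory p-value from Fisher's exact test, and report an exact or Firth-penalised odds ratio with its confidence interval. If covariate adjustment is wanted, a Firth penalised-likelihood test could replace Fisher, but choose one now. State that the named p-value alone decides the step, since an interval from another method may disagree at the margin.
- **8.2.6 (25% and 50%):** keep baseline-adjusted logistic regression, with region in place of center to agree with SAP 6.5, and name the test.
- **12:** record that logistic regression replaces the protocol's Fisher option at 25%, and that the 50% and 75% thresholds are additions.

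The cost is SAP wording and standard procedure options, with no new data. Fisher p-values for the rare endpoints are not covariate-adjusted, and the change does not make the remission step likely to pass.
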